7.2 Adjustments for Covariates

No adjustments for covariates are planned as this is a single-arm study.

7.3 Handling of Dropouts or Missing Data

No imputations will be used in analyses/summaries. However, a LOCF analysis will be used for evaluation of the Cdiff32 scores. Missing safety data will not be imputed beyond the adjustments for adverse event data mentioned in **Section 6.4.3**.

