11.8. Causality

For all adverse events, the investigator must pursue and obtain adequate information to determine the outcome of the adverse event and to assess whether the AE meets the criteria for classification as an SAE, serious suspected adverse reaction, suspected adverse reaction, unexpected AE, or unexpected suspected adverse reaction. For all AEs, sufficient information should be obtained by the investigator to determine the causality of the AE. For AEs with a causal relationship to the IP or the enema procedure, follow-up by the investigator is required until the event or its sequelae resolve or stabilize at a level acceptable to the investigator.

The investigator will make a causality assessment for all AEs and decide whether there is a reasonable possibility that the AE may have been caused by the study product or procedure, including an assessment of biologic plausibility, presence or absence of alternative causal explanations (such as continuation or exacerbation of the subject's recurrent CDI symptoms), and temporal relationship to product administration and/or the procedure. Relatedness to RBX2660 or the enema procedure is defined as:

- Unrelated: The event is due to an underlying or concurrent illness or effect of concomitant therapy and is not related to the study product or procedure (*e.g.*, has no temporal relationship to study product or procedure, or has a much more likely alternative etiology)
- Possible: There is some temporal relationship between the event and the administration of the study product or procedure, though the event could also be explained by the subject's medical condition or other therapies.
- Probable: The temporal relationship between the event and administration of the study product or procedure is suggestive, and the event is unlikely to be explained by the subjects' medical condition or other therapies alone.
- Definite: The event follows a reasonable temporal sequence from administration of the study product or procedure, follows a known or suspected response pattern to the study product and/or procedure, improves upon stopping the study product, and reappears upon repeated exposure, if that occurs.

If an investigator is unsure about whether to report a finding as an AE, they are encouraged to enter the finding as an AE into the study database.

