5.3 Analysis Populations

5.3.1 *Safety Population*

The safety population (SP) is defined as the population of subjects who had any treatment attempted or completed. The safety population will be used in analysis of all safety endpoints including the primary endpoint.

5.3.2 *Intent-to-Treat Population*

The ITT population is defined as all subjects enrolled, excluding screen failures.

5.3.3 *Modified Intent-to-Treat Population*

Analysis of the efficacy endpoints will use the modified Intent-to-Treat (mITT) population as a primary efficacy analysis population. The mITT population is defined as all subjects who successfully received treatment but excluding:

- subjects in whom treatment was attempted but not completed and;
- subjects who discontinue from the study prior to evaluation of treatment failure/success for the 8-week efficacy endpoint if the reason for exit is not related to CDI symptoms. Reason for exit will be

captured on the exit form to allow for identification of such subjects. Examples of reasons unrelated to CDI symptoms may include:

- Withdrawal of consent
- Death unrelated to CDI

5.3.4 *Per-Protocol Population*

The per-protocol (PP) population will consist of all subjects who successfully received treatment analyzed according to the treatment they received, excluding:

- Subjects who have documented protocol deviations to inclusion or exclusion criteria.
- Subjects who exited prior to the 8-week efficacy evaluation if the reason for exit was not related to CDI symptoms in the same manner as the mITT population.

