5.4 Safety Variables

Assessment of the primary safety objective and other safety objectives will be performed on all subjects exposed to RBX2660 (Safety Population, see Section 6.3.1), and will include descriptive statistics. Additional sub-analyses of safety data may be performed on sub-populations.

5.4.1 *Primary Safety Endpoint*

Number of subjects with investigational product- and/or enema-related treatment-emergent adverse events (TEAEs).

5.4.2 *Other Safety Endpoints*

1. Number of adverse events per subject
2. Timing of attributable TEAEs
3. Duration of TEAEs
4. Relatedness of TEAEs
5. Severity of TEAEs
6. Causality of TEAEs to IP, enema, *C. difficile* or prior condition
7. Number of each of the following CDI-related TEAEs through 8-weeks post treatment: death, septic shock, toxic megacolon, colonic perforation, emergency colectomy, and intensive care unit (ICU) admission
8. Onset of new chronic conditions relative to treatment administration

5.4.3 *Adverse Events*

An adverse event (AE) is any untoward medical occurrence associated with the use of IP, whether or not the event is considered product-related. Preexisting conditions that worsen in frequency, intensity or character of the condition during study participation will be recorded as an AE. AEs will be recorded for each subject from the day of enrollment through the 6-month telephone assessment. Serious adverse events (SAEs) will be recorded for each subject from the day of enrollment through the duration of the study.

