5.4.3.2 Adverse Event Severity

Severity of AEs will be graded as mild, moderate, severe, or potentially life-threatening. The severity grade of events for which the investigator did not record severity will be categorized as “Unknown” for tabular summaries and data listings and will be considered the least severe for the purposes of sorting for data presentation. For summaries by severity grade, if a subject has multiple events occurring in the same SOC or PT, then the most severe event will be selected.

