5.4.3.3 Relationship of Adverse Events to Study Treatment

Relationship of an AE to the Investigational Product (IP), the enema procedure, *C. difficile* disease, and a preexisting condition will be classified by the investigator as definite, probable, possible, or unrelated. Related events will include AEs that are classified as definitely, probably, or possibly related.

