5.4.3.4 Treatment-Emergent Adverse Events

Adverse events will be considered treatment-emergent adverse events (TEAE) according to the following algorithm:

- If the complete onset date of an AE is known, then:
 - If AE onset date is prior to initial treatment date, then the AE will not be considered treatment-emergent.

- If AE onset date occurs after IP exposure on or after initial treatment date, then the AE will be considered treatment-emergent.
 - If AE onset date is partially known, then:
 - If day is unknown, and month/year occurs on or after first enema month/year, then AE will be considered treatment-emergent. Otherwise, AE will not be considered treatment-emergent.
 - If month/day is unknown, and year occurs on or after first enema year, then AE will be considered treatment-emergent. Otherwise, AE will not be considered treatment-emergent.

5.4.4 *Other Observations Related to Safety*

5.4.4.1 *Solicited Adverse Events*

The following list of anticipated adverse events are solicited from subjects via the Subject Diary from the date of enrollment through the 7th day after receiving the study treatment.:

- gas (flatulence)
- abdominal distension or bloating
- rectal irritation or pain
- chills/severe shivering
- abdominal pain or cramping
- increased diarrhea
- constipation
- rectal bleeding
- nausea
- vomiting
- fever $\geq 37.8^{\circ}\text{C}$ ($\geq 100.0^{\circ}\text{F}$)

Frequency and severity of the solicited AEs will also be captured in the Subject Diary.

5.4.4.2 *Major Complications of CDI Events*

Frequencies of major complications of CDI including death, septic shock, toxic megacolon, colonic perforation, emergency colectomy, or ICU admission will be collected through the 6-month telephone assessment after the last study enema.

5.4.4.3 *Hospitalizations for Recurrent CDI*

Details regarding hospitalizations due to CDI, including admission and discharge date/time, reason for admission, whether the subject was admitted to an ICU, and ICU admission and discharge date/time (if applicable), will be collected following both the first and second study enemas

5.5 **Efficacy Variables**

5.5.1 ***Efficacy Endpoint***

Assessment of secondary objectives will include descriptive statistics and be performed on pre-defined analysis populations including Intent-to-Treat (ITT), modified Intent-to-Treat (mITT) and Per-Protocol (PP). Additional sub-analyses of safety data may be performed on sub-populations.

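### Read literally, the SAP leaves adverse events with no relatedness rating, and enema events before or without product delivery, out of the primary safety count

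*SAP*

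**What the plan says.** The primary endpoint (SAP 5.4.1) is "Number of subjects with investigational product- and/or enema-related treatment-emergent adverse events (TEAEs"), summarised descriptively in the Safety Population (SAP 6.6.1). That population is "the population of subjects who had any treatment attempted or completed" (SAP 5.3.1).

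On relatedness, SAP 5.4.3.3 gives four ratings for each of four factors, two of which are the product and the enema procedure. It then states: "Related events will include AEs that are classified as definitely, probably, or possibly related". It does not mention a missing rating. SAP 7.3 says: "Missing safety data will not be imputed beyond the adjustments for adverse event data mentioned in" Section 6.4.3. For severity, by contrast, SAP 5.4.3.2 does have a missing-value rule: "The severity grade of events for which the investigator did not record severity will be categorized as" Unknown.

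On treatment emergence, SAP 5.4.3.4 has two branches for a complete onset date. Onset before the initial treatment date is not treatment-emergent. The other branch reads: "If AE onset date occurs after IP exposure on or after initial treatment date, then the AE will be considered treatment-emergent". The partial-date rules compare the onset month or year with that of the first enema and do not mention exposure.

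**The concern.** The primary analysis has no comparator, test or threshold. The definitions of related and treatment-emergent therefore decide the result, and an event that fails either one does not reach the numerator while its subject stays in the denominator.

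Both gaps act in the favourable direction for a safety endpoint. An unrated event cannot meet the definition of related, and the bar on imputation stops the analyst from treating it cautiously. The exposure condition is a poor match for an endpoint that explicitly includes enema-related events. Protocol 11.3 anticipates rectal pain, rectal bleeding and intestinal puncture, any of which could arise before product flows. Protocol 10.8 records separately enemas that were attempted but unfinished and those opened but not given, so the plan expects such cases.

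**Working it through.** The plan states no figure to reproduce: 750 is a cap with no power calculation (SAP 3.3). The check is a reading of the rules, followed by a rough scale.

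**Unrated event.** Take a TEAE with no rating for product or enema.
- SAP 5.4.3.3: it is not rated definite, probable or possible, so it is not in the related set. It is not rated unrelated either.
- SAP 7.3: no value may be filled in.
- SAP 6.6.2.1: the causality table takes each subject's highest association, and a missing rating has no place in that order.
- Result: it is not counted in the primary endpoint, unless the subject has another related TEAE.

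**Event on the enema day before delivery.**
- First branch: onset is not before the treatment date, so the event is not excluded.
- Second branch: onset is not after exposure, so it is not included.
- SAP Table 3 places day 1 after baseline, and SAP 6.6.2.1 has an interval for onset on the enema date. Both go by calendar date and would treat the event as post-baseline.
- Result: unclassified.

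**Fully dated event after an attempt that delivered no product.** It fails both branches for the same reason, on any later day. A partly dated event in the same subject, in or after the enema month, would count. The plan thus treats the better-documented event less inclusively.

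**Scale.**
- Base rate, from retrospective study 2019-02 (Protocol 5.3.5): 11 subjects (17.2%) had product-related TEAEs and 3 (4.7%) enema-related ones. The implied N is 11/0.172 = 64.0. The combined rate lies between 11/64 = 17.2% (full overlap) and 14/64 = 21.9% (no overlap), or about 129 to 164 of 750.
- One missed subject: 1/750 = 0.13 points.
- Unrated events: let u be the share of subjects whose only candidate TEAEs are unrated. The documents give no value, so u is assumed.

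| u (assumed) | subjects added, 750 × u | rate on 17.2% base | rate on 21.9% base |
|---|---|---|---|
| 0 | 0 | 17.2% | 21.9% |
| 0.5% | 3.75 | 17.7% | 22.4% |
| 1% | 7.5 | 18.2% | 22.9% |
| 2% | 15 | 19.2% | 23.9% |

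- Incomplete enemas, from study 2014-01 (Protocol 5.3.2): 128 in the safety population, 127 completing at least one enema. 1/128 = 0.78%, and 750 × 1/128 = 5.9. If 10% to 100% of these subjects had a related event only before delivery (assumed), 0.6 to 5.9 subjects would be missed, or 0.1 to 0.8 points.
- For comparison, the 95% half-width at n = 750 is 1.96 × √(0.172 × 0.828/750) = 2.7 points at the lower base rate.

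**The case against.** The case against has real force on four points.

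- **Missing ratings should be rare.** Protocol 11.8 says: "The investigator will make a causality assessment for all AEs". Protocol 13.7 adds investigator review and signature of every eCRF and ongoing data review. This stands. It limits the size of the gap but supplies no rule for the cases that remain.
- **A same-day event may be counted in practice.** The algorithm works on dates, the documents mention an onset date but no onset clock time (Protocol 11.13), and the onset intervals are date-based. This also stands for enemas that were then completed. It does not help where no product was delivered, and it leaves the decision to programming.
- **The scale is weak.** The one incomplete case in study 2014-01 is described among subjects exposed to an enema. It is not a documented no-product case, and no pre-delivery event is reported for it. The 6 of 750 is only a rough scale for incomplete enemas.
- **The direction is not one-sided.** A subject with any other related TEAE is still counted, and the inclusive partial-date rules push the count upward by an unknown amount.

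A reader might infer that the SAP codes unrated events as unrelated, or declares pre-delivery events not treatment-emergent. It does neither. It is silent on the first, and SAP 7.1 bases categorical summaries on non-missing subjects. It leaves the second unclassified. Nor is it established that a subject whose enema was opened but not given belongs to the Safety Population: SAP 5.3.1 says attempted or completed, while SAP 5.4 describes the same population as exposed. The events themselves are not lost, since all AEs are listed (SAP 6.6.2.1).

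A reader might also want ungraded events ranked as severe, because an ungraded event "will be considered the least severe for the purposes of sorting for data presentation" (SAP 5.4.3.2). Severity is not part of the primary endpoint and ungraded events are already shown as Unknown. Ranking them as severe would impute a grade, so no change is needed there.

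**Conclusion.** The point holds as two unhandled cases, each of which falls outside the primary count when the text is read literally. The count could be slightly understated; the documents do not show that it is. With an assumed 0 to 2% of subjects having only unrated candidate events, the effect is 0 to 2 points on a base of about 17 to 22%, less than the 2.7-point sampling half-width. Attempts that deliver no product can be scaled only roughly, from about 6 incomplete enemas in 750. Pre-delivery events in completed enemas are not covered by any figure. No decision threshold depends on these amounts. The reason to act is that the rules define the primary safety result and can be settled cheaply before the final analysis.

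**What to change.** 1. **SAP 5.4.3.3 and 7.3:** count a TEAE with missing relatedness to the product or to the enema as related to that factor. Footnote how many there were, and give a sensitivity count of the primary endpoint without them. State in 7.3 that this is an exception to the bar on imputation.
2. **SAP 5.4.3.4:** define treatment-emergent as onset at or after the start of the first enema attempt, whether or not product was delivered. If onset is recorded by date only, say how same-day events are assigned; counting them would agree with Table 3.
3. **SAP 7.3:** correct the cross-reference from 6.4.3 to 5.4.3. Section 6.4 covers demographics.

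The cost is a few SAP sentences, a footnote and one extra count, with no new data. The reported rate may rise slightly, and some unrated events counted as related will in truth be unrelated. The sensitivity count shows how much that matters.

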7.4 Safety Oversight

The Medical Monitor provides review of serious adverse events or events reported by the site as related to the investigational product or enema procedure to assess accuracy of reporting as related to seriousness and causality, and periodic review of adverse events for trends. Details of this review are documented in a Safety Management Plan. The Medical Monitor's review will be provided to the DSMB for analysis purposes and as applicable for the proper adjudication of potential study stopping rules (see **Section 8.5.1**).

7.5 Final Analyses and Data Monitoring

A final analysis and report will be completed once the last subject has completed the 6-month follow-up visit for their study treatment, including 6-month follow-up after a second RBX2660 study treatment, if applicable.

7.5.1 Study Stopping Rules

Enrollment will be paused if any of the following events are identified and the DSMB determines that there is probable cause that the IP or enema procedure contributed to the event:

1. There is probable cause that IP or enema procedure (e.g., due to transfer from an RBX2660 donor) contributed to a pathogenic intestinal infection in the stool of any subject, or
2. Any series of events of major significance such as death or other serious outcome for which a causal connection with the IP is plausible and represents an excess of the important adverse event(s).

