Statistical Considerations	The primary safety analysis will be performed on all subjects exposed to RBX2660 and will include descriptive statistics. Additional sub-analyses of safety data may be performed on sub-populations. Efficacy analyses will be performed on pre-defined analysis populations including Intent-to-Treat (ITT) and modified Intent-to-Treat (mITT). A final analysis of safety and efficacy results will be analyzed and reported in a final report after the last subject has completed the 6-month follow-up visit for their study treatment, including 6-month follow-up after a second RBX2660 study treatment, if applicable.

Study Stopping Rules	
The DSMB will determine whether enrollment will be paused, the study terminated, or other action taken based on their assessment that:
 
• There is probable cause that the IP or enema procedure (e.g., due to transfer from an RBX2660 donor) contributed to a new pathogenic intestinal infection in the stool of any subject; or• Any events of major significance such as death or other serious outcome for which a causal connection with the IP is plausible and represents an excess of the important adverse event(s). 
In the event that one of the preceding rules appears to be met based on site reported data and/or Medical Monitor review, the Rebiotix Operations Department will review the donor history and batch processing/release records for the product unit(s) administered in these cases. A report of the review will be forwarded to the DSMB Chair for review. If probable cause is suspected, the DSMB Chair will convene the entire DSMB for event review.
 
Upon the DSMB's determination of action, the Chair will notify Rebiotix, who will notify the study sites. If enrollment is stopped, Rebiotix and the study sites will assess for the occurrence of similar events and evaluate IP and study records for possible root cause(s). Enrollment may be re-started upon further review and approval from the DSMB. As appropriate, the DSMB may recommend study termination or measures short of termination with the objective of reducing the risk of adverse events. Details regarding DSMB responsibilities will be provided in the DSMB Charter.

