11.13. Study Stopping Rules for Safety

Rebiotix will oversee review of all AEs reported during the study to observe for trends and unanticipated events, either in severity, seriousness or incidence, and to assess if a study stopping rule may be triggered. AE review includes the event description, onset date in relation to the treatment date, and the investigator's determination of causal relatedness to IP, the enema procedure, and pre-existing condition, as well as rating the event's severity and seriousness. Additionally, the Medical Monitor assessment of seriousness and causality will be provided and reviewed as it may be different from the site investigator report of the event. Anticipated AEs may trigger the study stopping rules.

The DSMB will determine whether enrollment should be paused, the study terminated, or other actions taken based on their assessment that:

- a) There is probable cause that IP or enema procedure (e.g., due to transfer from an RBX2660 donor) contributed to a pathogenic intestinal infection in the stool of any subject, or
- b) Any events of major significance such as death or other serious outcome for which a causal connection with the IP is plausible and represents an excess of the important adverse event(s).

To support the DSMB assessment, the Rebiotix Operations Department may be asked to review the donor history and batch processing/release records for the product unit(s) administered in these cases, and forward its report to the DSMB Chair for review. The DSMB Chair will review the Operations Department report. If probable cause is suspected, the DSMB Chair will convene the entire DSMB for event review.

Upon the DSMB's determination of action, the Chair will notify Rebiotix, who will notify the study sites.

If enrollment is stopped, Rebiotix and the study sites will assess for the occurrence of similar events, and evaluate IP and study records for possible root cause(s). Enrollment may be re-started upon further review and approval from the DSMB. As appropriate, the DSMB may recommend study termination or measures short of termination with the objective of reducing the risk of AEs.

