The site investigator will make the initial determination of treatment success or failure based on the protocol-defined study definitions. The site investigator's assessment will then be provided to the Endpoint Adjudication Committee for independent adjudication of treatment success or failure that will be utilized for study analysis and reporting purposes. This may be done in an ongoing basis or a single meeting. Details of the EAC logistics, activity and responsibilities will be included in an EAC charter.

3.2 **Blinding**

This study is not blinded.

3.3 **Determination of Sample Size**

The purpose of this study is to assess the safety and tolerability of RBX2660 in a recurrent CDI population that is broader and more inclusive than that included in prior studies using RBX2660. In order to continue to collect prospective safety information and allow open-label treatment access to a broader population of patients, up to 750 subjects will be treated with RBX2660. As an open-label study, there are no statistical powering considerations for the revised sample size.

Subjects who have signed informed consent forms but do not meet all eligibility criteria will be considered screen failures. Subjects who withdraw for any reason prior to administration of the enema will be replaced without counting toward the sample size treatment cap of 750 subjects.

3.4 **Treatment**

Active treatment consists of one dose of RBX2660 delivered via enema.

4 **CHANGES IN THE CONDUCT OF THE STUDY OR PLANNED ANALYSES**

4.1 **Changes in the Conduct of the Study**

There have been no changes to the conduct of the study or planned analysis, however, ad hoc analyses may be performed as needed to support regulatory review.

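### SAP 7.5.1 restates the protocol's stopping rule for deaths and other serious outcomes with an extra probable-cause condition and a requirement for a series of events

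*SAP*

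**What the plan says.** Protocol 11.13 opens with "The DSMB will determine whether enrollment should be paused, the study terminated, or other actions taken based on their assessment that", and two rules follow. Rule (a) concerns a pathogenic intestinal infection and asks for probable cause. Rule (b) reads "Any events of major significance such as death or other serious outcome for which a causal connection with the IP is plausible" and adds that there must be an excess of the important adverse events. The synopsis gives the same pair with the same two standards.

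SAP 7.5.1 has a different lead-in. Enrollment is to be paused if any listed event is identified and "the DSMB determines that there is probable cause that the IP or enema procedure contributed to the event". Item 1 matches rule (a). Item 2 reads "Any series of events of major significance such as death or other serious outcome for which a causal connection with the IP is plausible", again with an excess.

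SAP 4.1 states "There have been no changes to the conduct of the study or planned analysis". SAP 7.4 sends the Medical Monitor's review to the DSMB "as applicable for the proper adjudication of potential study stopping rules" and points to the SAP's own stopping-rule section (printed there as 8.5.1).

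On calling the board together, the synopsis starts a review of donor and batch records "In the event that one of the preceding rules appears to be met based on site reported data and/or Medical Monitor review". Both the synopsis and 11.13 then say "If probable cause is suspected, the DSMB Chair will convene the entire DSMB for event review".

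**The concern.** The two rules use two different words for causality, side by side in one list, which suggests a deliberate distinction: a looser causal test where the outcome may be death, balanced by the need for an excess. The SAP lead-in removes it. If probable cause must always be found, the word plausible in item 2 does no work.

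What is at stake is a written safety threshold. For one pattern of deaths or serious outcomes, a reader who starts from the SAP and a reader who starts from the protocol could disagree on whether the pause criterion has been reached. The study enrols a broader population than earlier studies of the product, and protocol 5.4 says its risk profile has not been well characterized. The wording should therefore be the same in both documents.

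**Working it through.** No sample size, error rate or numerical boundary is involved, so the check is a comparison of texts.

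**Step 1. Conditions stated for each rule.**

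| Text | Infection | Death or other serious outcome |
|---|---|---|
| Protocol 11.13 and synopsis | probable cause | plausible link to the IP + excess |
| SAP 7.5.1, numbered item alone | probable cause | plausible link to the IP + excess, in a series of events |
| SAP 7.5.1, lead-in and item together | probable cause, stated twice | plausible link + excess, in a series, + probable cause |

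For infection the lead-in is only redundant. For deaths and serious outcomes it adds a condition.

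**Step 2. Where the answers differ.** Take probable cause to be stricter than plausible, as in ordinary usage; neither document defines either term.

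| DSMB's view of the events | Protocol rule (b) | SAP lead-in + item 2 |
|---|---|---|
| Link not plausible | not met | not met |
| Link plausible, no excess | not met | not met |
| Plausible but short of probable cause, with an excess | met | not met |
| Probable cause, with an excess, in a series | met | met |

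The third row is the causal conflict. The words requiring a series open a second, smaller gap: events that the board regards as an excess but not as a series meet rule (b) and do not, on its face, meet item 2.

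**Step 3. Could this be an intended change?** SAP 4.1 reports none. Nothing in SAP 7.4 or 7.5.1 says that the protocol's standard is being tightened. It reads as an inexact restatement.

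**Step 4. Which text controls?** Protocol 11.11 describes the DSMB's power to stop the study as resting on the rules that the protocol defines. That favours rule (b) as written in 11.13. SAP 7.4 nevertheless sends the reader of the SAP to the SAP's own version.

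**Step 5. The convening sentence.** In the synopsis the records review can start under either rule, yet the only written duty to call the full board is worded in rule (a)'s terms. In 11.13 the DSMB is first given both rules to assess, the records review is optional support, and the convening sentence closes that supporting paragraph. The mismatch is therefore one of wording and is weaker than the SAP conflict.

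**The case against.** The best reply is that the SAP does not control this decision. Protocol 11.11 binds the board to the protocol's rules, and SAP 4.1 fits a loose summary better than a rival standard. This stands, and it is the main reason the point is minor. It does not make the SAP text correct: if the protocol governs, the SAP should say the same thing.

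A reader might infer that the SAP forbids a pause unless probable cause is found. It does not. It says when enrollment will be paused, using if and not only if, so the wider discretion in 11.13 is untouched.

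A reader might also infer that the full DSMB cannot be called for a rule (b) signal. The documents do not support that either. Suspicion of probable cause is a low trigger, nothing stops the Chair from convening on other grounds, and meeting timing is left to a charter that is not among the documents and may contain further triggers.

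Finally, it is tempting to equate probable cause with the causality grade Probable in protocol 11.8, and then to count how many earlier serious events would have passed or failed. Nothing in the documents makes that link, and rule (b) also needs an excess, so such a count would not measure this defect.

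Other safeguards also operate. SAEs are reported within 24 hours, the sponsor reviews all AEs for possible stopping triggers, and the Medical Monitor confers with the DSMB as applicable on safety concerns. They lower the practical risk but do not correct the SAP's statement of the rule.

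**Conclusion.** SAP 7.5.1 is wrong as written. Its lead-in contradicts the causal standard in its own item 2, and both the lead-in and the series wording depart from protocol rule (b) without a declared change. The causal conflict affects one class of cases: deaths or serious outcomes in excess, with a link that the board finds plausible but does not raise to probable cause.

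The conclusion assumes that the two undefined terms differ in strength. If the sponsor means them as synonyms, the causal conflict disappears, but the use of both within one list speaks against that. The series wording remains a difference in either case.

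The weight is minor. The board works from the protocol's rules, and the documents do not show that any pause would be prevented. No frequency can be attached to the gap. The convening sentence deserves at most a clarification.

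**What to change.** In SAP 7.5.1:

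- Delete the condition "the DSMB determines that there is probable cause that the IP or enema procedure contributed to the event" and let the lead-in read: *Enrollment will be paused if the DSMB determines that either of the following is met:*
- Keep probable cause in item 1, and the plausible link plus an excess in item 2.
- Delete the two words in item 2 that require a series.
- Add a sentence that protocol 11.13 governs, including the DSMB's options to terminate the study or take other action.

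This keeps the SAP's firm statement that enrollment will be paused. Copying the whole 11.13 lead-in would lose that statement, including for infection, where the two causal standards already agree.

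Optionally, and only as a clarification, extend the convening sentence in the synopsis and 11.13 so that the Chair's duty also arises when rule (b) appears to be met.

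The SAP change is a short wording edit with no effect on data collection, analysis or staffing. The optional change touches the protocol and needs the approvals described in 13.14, so it is best held for the next amendment. It might lead to some additional meetings of the existing board, and the documents do not allow a reliable estimate of how many.
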